## 6.2.2 Phase 2 Screening Procedures

The following procedures must be conducted  $\leq 4$  weeks prior to the first dose of study product:

- Written informed consent
- Verify eligibility criteria
- Patient demographics
- Pathology Review
  - Verification of Bladder Cancer Staging at the time of the baseline staging procedure (refer to Appendix 1) *High-risk or intermediate-risk non-muscle invasive disease must be histologically/cytologically confirmed. There will be no central pathology review. In the event that multiple diagnostic procedures are performed for this occurrence of disease, dates of all procedures will be captured.*
  - Verification of cancer sub-type (transitional cell carcinoma, squamous cell carcinoma, adenocarcinoma or undifferentiated carcinoma)
  - Verification of the date of baseline staging procedure (must be within 6 weeks)
- Physical examination (including weight, vital signs [heart rate, temperature, respiratory rate and blood pressure])
- 12-lead electrocardiogram (ECG)

The following procedures must be conducted  $\leq 2$  weeks prior to the first dose of study product:

- Medical history, including concomitant medications within 14 days of first dose
- Hematology, chemistry with LDH, and dipstick urinalysis
- Urine or serum pregnancy test for female patients of childbearing potential

## 6.2.3 Phase 2 On-Study Procedures

Study-related procedures and assessments performed during treatment on study are detailed as follows and in the Schedule of Events table (see Section 6.2.1).

### 6.2.3.1 Phase 2 Baseline Assessments (Day -3 to Day 1)

The following activities may be performed within three days of enrollment/randomization or on Day 1 prior to enrollment/randomization:

- Update of medical history including concomitant medications
- Blood and urine collection for immune monitoring
- Physical examination (symptoms, weight, vital signs only if screening exam performed more than three days prior to first dose)
- Hematology, chemistry with LDH, and dipstick urinalysis (unless screening labs obtained within three days of first dose)
- Urine or serum pregnancy test for female patients of childbearing potential (unless screening labs obtained within three days of first dose)

- Autoimmune Labs (ANA, TSH, ESR, and C-reactive protein are required; RF, T3, T4, and thyroid antibodies if clinically indicated)
- Autoimmune Phenomena – Assessment of adult autoimmune system disorders (including: eye exam for dry eyes, lymph node and joint assessment for swelling, and skin exam for vitiligo and rash)

Once the patient has met all of the eligibility requirements for the study, patients who will receive BCG will be randomized (treatment assigned within IWRS). Each patient will be considered enrolled in the study at the time of first dose.

#### **6.2.3.2 Phase 2 Assessments at Week 1 (Day 1)**

The following procedures will be performed after all the previous baseline procedures have been completed:

- Study product administration
  - Initiate series of weekly study product dosing (dosing should begin within 6 weeks of baseline staging procedure)
  - Initiate series of weekly BCG dosing (Arms 1-3 only)
  - Monitor patient on site for potential acute reactions for 30 minutes after study product administration
- Record adverse events
- Record concomitant medications
- Send at least 4, non-stained, 10 micron sections from baseline staging procedure for evaluation of antigen expression. If slides are not available, formalin-fixed, paraffin-embedded (FFPE) tissue ( $\geq 50$  microns) is also acceptable.

#### **6.2.3.3 Phase 2 Assessments at Week 2 (Day 8) through Week 6 (Day 36)**

The following procedures will be performed at each of the weekly visits for Week 2 (Day 8  $\pm 1$ ), Week 3 (Day 15  $\pm 1$ ), Week 4 (Day 22  $\pm 1$ ), Week 5 (Day 29  $\pm 1$ ), and Week 6 (Day 36  $\pm 1$ ):

- Study product administration
  - Weekly study product dosing
  - Weekly BCG dosing (Arms 1-3 only)
  - Monitor patient on site for potential acute reactions for 30 minutes after study product administration
- Record adverse events
- Record concomitant medications

#### **6.2.3.4 Phase 2 Assessments at Week 7 (Day 43 $\pm 1$ )**

The following procedures will be performed at this visit:

- Blood and urine collection for immune monitoring collected prior to dosing
- Study product administration
  - Weekly study product dosing

- Monitor patient on site for potential acute reactions for 30 minutes after study product administration
- Record adverse events
- Record concomitant medications

#### **6.2.3.5 Phase 2 Assessments at Week 8 (Day 50) through Week 12 (Day 78)**

The following procedures will be performed at each of the weekly visits for Week 8 (Day 50 ±1), Week 9 (Day 57 ±1), Week 10 (Day 64±1), Week 11 (Day 71±1), and Week 12 (Day 78±1):

- Study product administration
  - Weekly study product dosing
  - Monitor patient on site for potential acute reactions for 30 minutes after study product administration
- Record adverse events
- Record concomitant medications

#### **6.2.3.6 Phase 2 Assessments at Week 13 (Day 85±1)**

The following procedures will be performed at this visit:

- Physical exam (symptoms, weight and vital signs only)
- Blood and urine collection for immune monitoring
- Hematology, chemistry with LDH, and dipstick urinalysis
- Cystoscopy/Cytology and, if indicated, a repeat biopsy – per SOC to evaluate for evidence of disease. *Note: Patients with evidence of disease may continue on treatment if judged by the investigator to be in the patient's best interest. Patients who discontinue study treatment will continue in long-term follow-up. If biopsy was performed, provide at least 4, non-stained, 10 micron sections for TCR sequencing and analysis of infiltrating T-cells. If slides are not available, FFPE tissue (≥50 microns) is also acceptable.*
- Autoimmune Phenomena – Assessment of adult autoimmune system disorders (including: eye exam for dry eyes, lymph node and joints assessment for swelling, and skin exam for vitiligo and rash)
- Record adverse events
- Record concomitant medications

#### **6.2.3.7 Phase 2 Assessments at Week 14 (Day 92) through Week 16 (Day 106)**

The following procedures will be performed at each of the weekly visits for Week 14 (Day 92 ±1), Week 15 (Day 99 ±1), and Week 16 (Day 106 ±1):

- Study product administration
  - Weekly study product dosing
  - Weekly BCG dosing (Arms 1-3 only)
  - Monitor patient on site for potential acute reactions for 30 minutes after study product administration

- Record adverse events
- Record concomitant medications

#### **6.2.3.8 Phase 2 Assessments at Week 25 (Day 169)**

The following procedures will be performed at the visit for Week 25 (Day169±3):

- Hematology, chemistry with LDH, and dipstick urinalysis
- Cystoscopy/Cytology and, if indicated, a repeat biopsy – per SOC to evaluate for recurrent disease. *Note: Patients with evidence of disease may continue on treatment if judged by the investigator to be in the patient’s best interest. Patients who discontinue study treatment will continue in long-term follow-up. If biopsy was performed, provide at least 4, non-stained, 10 micron sections for TCR sequencing and analysis of infiltrating T-cells. If slides are not available, FFPE tissue (≥50 microns) is also acceptable.*
- Record adverse events
- Record concomitant medications

#### **6.2.3.9 Phase 2 Assessments at Week 26 (Day 176) and Week 27 (Day 183)**

The following procedures will be performed at each of the weekly visits for Week 26 (Day 176±3) and Week 27 (Day 183±3):

- Study product administration
  - Weekly study product dosing
  - Weekly BCG dosing (Arms 1-3 only)
  - Monitor patient on site for potential acute reactions for 30 minutes after study product administration
- Record adverse events
- Record concomitant medications

#### **6.2.3.10 Phase 2 Assessments at Week 28 (Day 190±3)**

The following procedures will be performed at this visit:

- Blood and urine collection for immune monitoring collected prior to dosing
- Study product administration
  - Weekly study product dosing
  - Weekly BCG dosing (Arms 1-3 only)
  - Monitor patient on site for potential acute reactions for 30 minutes after study product administration
- Record adverse events
- Record concomitant medications

### **6.2.3.11 Phase 2 Assessments at Week 37 (Day 253)**

The following procedures will be performed at the visit for Week 37 (Day 253±3):

- Hematology, chemistry with LDH, and dipstick urinalysis
- Cystoscopy/Cytology and, if indicated, a repeat biopsy – per SOC to evaluate for recurrent disease. *Note: Patients with evidence of disease may continue on treatment if judged by the investigator to be in the patient's best interest. Patients who discontinue study treatment will continue in long-term follow-up. If biopsy was performed, provide at least 4, non-stained, 10 micron sections for TCR sequencing and analysis of infiltrating T-cells. If slides or curls or fresh frozen specimens are not available, FFPE tissue (≥50 microns) is also acceptable.*
- Record adverse events
- Record concomitant medications

### **6.2.3.12 Phase 2 Assessments at Week 49 (Day 337)**

The following procedures will be performed at the visit for Week 49 (Day 337±3):

- Hematology, chemistry with LDH, and dipstick urinalysis
- Cystoscopy/Cytology and, if indicated, a repeat biopsy – per SOC to evaluate for recurrent disease. *Note: Patients with evidence of disease may continue on treatment if judged by the investigator to be in the patient's best interest. Patients who discontinue study treatment will continue in long-term follow-up. If biopsy was performed, provide at least 4, non-stained, 10 micron sections for TCR sequencing and analysis of infiltrating T-cells. If slides or curls or fresh frozen specimens are not available, FFPE tissue (≥50 microns) is also acceptable.*
- Record adverse events
- Record concomitant medications

### **6.2.3.13 Phase 2 Assessments at Week 50 (Day 344) through Week 52 (Day 358)**

The following procedures will be performed at each of the weekly visits for Week 50 (Day 344±3), Week 51 (Day 351±3), and Week 52 (Day 358±3):

- Study product administration
  - Weekly study product dosing
  - Weekly BCG dosing (Arms 1-3 only)
  - Monitor patient on site for potential acute reactions for 30 minutes after study product administration
- Record adverse events
- Record concomitant medications

### **6.2.3.14 Phase 2 Week 56 (Day 386 ±3) – End of Treatment Visit (4 weeks post last dose)**

The following procedures should be completed approximately four weeks following last dose of study product including patients who discontinue study product dosing prematurely.

- Physical exam (full examination as well as weight and vital signs)
- 12-lead ECG

- Blood and urine collection for immune monitoring
- Hematology, chemistry with LDH, and dipstick urinalysis
- Urine or serum pregnancy test for female patients of childbearing potential
- Autoimmune Labs (ANA, TSH, ESR, and C-reactive protein are required; RF, T3, T4, and thyroid antibodies if clinically indicated)
- Autoimmune Phenomena – Assessment of adult autoimmune system disorders (including: eye exam for dry eyes, lymph node and joint assessment for swelling, and skin exam for vitiligo and rash)
- Record concomitant medications
- Record adverse events

### 6.3 Long-term Follow-up Visits

All patients will be followed for the procedures listed below every 3 months from the date of the previous visit for 2 years then every 6 months from the date of the previous visit for a year or until study termination, whichever occurs first:

- Survival
- New anticancer treatments initiated after disease recurrence
- TURBT or fulguration procedures
- Cystectomy

In addition patients who have completed all study treatments or have discontinued study product dosing due to reason other than disease recurrence/progression will have the following procedures performed at each long-term follow-up visit:

- Cystoscopy/Cytology; biopsy if area suspicious for disease recurrence is identified at discretion of investigator (*Note: patients who have a biopsy performed will provide at least 4, non-stained, 10 micron sections for TCR sequencing and analysis of infiltrating T-cells.*) *If slides are not available, FFPE tissue (≥50 microns) is also acceptable.*

If a patient has recurrent/progressive disease and discontinues study treatment, the above disease assessment procedures will be discontinued, and subsequent long-term follow-up visits may be conducted via phone visit.

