## 2.2 Secondary Objectives

- To evaluate the safety of the combination of vesigenurtacel-L and BCG (Phase 2 only)
- To evaluate the safety of high dose vesigenurtacel-L monotherapy (Phase 2 only)
- To evaluate the proportion of patients with recurrence at 3, 6, 12, 18, and 24 months
- To evaluate the proportion of patients with progressive disease at 3, 6, 12, 18, and 24 months
- To evaluate disease-free survival at 3, 6, 18, and 24 months
- To evaluate overall disease-free survival
- To evaluate overall survival (OS)
- To evaluate the proportion of patients undergoing post-treatment TURBT or fulguration by 12 and 24 months
- To evaluate the proportion of patients undergoing cystectomy by 12 and 24 months
- To evaluate the proportion of patients with immunologic response of PBMCs via intracellular cytokine staining (ICS) by flow cytometry and/or ELISPOT on CD8+ cells following vesigenurtacel-L vaccination

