All patients in both the Phase 1 and Phase 2 portions of the study will have a cystoscopy and cytology and, if clinically indicated, a biopsy performed approximately every 3 months for 2 years then every 6 months for up to a year, study termination, disease progression, or recurrence requiring treatment discontinuation, whichever occurs first. Patients with evidence of disease at an assessment may continue on treatment if judged by the investigator to be in the patient's best interest (e.g. would normally receive another course of BCG therapy as standard of care (SOC)). Upon discontinuation of study treatment, additional treatment will be at the discretion of the treating physician per SOC. While treatment may continue in the presence of evidence of disease, statistical analysis of disease-free status will still follow strict definitions as defined in section 10.1 Evaluation of Disease.

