### **7.2.2 Discontinuation from Study Follow-Up**

If a patient prematurely discontinues study treatment for any reason, the patient will continue to be followed for study endpoints, unless consent for this is specifically withdrawn. If the patient withdraws consent for continued follow up, the investigator must make every effort to perform the EOT assessments four weeks following the last dose of study product, even if the patient has initiated other anticancer treatment.

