7.2 Secondary Efficacy Analyses

For time-to-event endpoints (e.g. DFS, OS), Kaplan-Meier / product limit method will be used to estimate the survival distributions over time, and to estimate median time to event. Where appropriate, inference for time-to-event endpoints will be assessed using the Log-rank test statistic, and the treatment effect will be estimated using Cox proportional hazards model. The assumption of proportional hazards will be assessed graphically.

The following will be analysed using Kaplan-Meier time-to-event methodology:

- Time To Recurrence, defined as the time from randomization to recurrence.
 - Recurrence is defined as disease that has recurred to the same extent of disease (ie same stage / severity) or to a lower stage/severity of disease compared to screening.
 - If recurrence has not occurred in a patient, the date of last disease assessment will be used as the timepoint for censoring.
 - The analysis will be repeated in an exploratory manner where recurrence is defined as only those recurrences to the same extent of disease (or greater) as screening.

- Time To Progression, defined as the time from randomization to progression.
 - Progression is defined as an increase in T stage from CIS or Ta (at screening) to T1 (lamina propria invasion), development of T2 or greater or lymph node (N+) disease or distant metastasis (M1), or an increase in grade from low to high per the IBCG recommendations..
 - If progression has not occurred in a patient, the date of last disease assessment will be used as the timepoint for censoring.

- Disease-Free Survival, defined as the time from randomization to recurrence or progression.
 - If a patient has recurred or progressed, then the first date the recurrence or progression has occurred will be used as the timepoint for the event.
 - If a patient has neither recurred nor progressed, then the date of last disease assessment will be used as the timepoint for censoring.

- Overall Survival, defined as the the time from randomization to death.
 - If a patient is still alive, then the patient will be censored on the date of most recent date known alive.
 - If a patient is lost to follow up, then the patient will be censored on the date last known alive.

- Time to cystectomy, defined as the time from randomization to cystectomy.
 - If a patient has not undergone cystectomy, the patient will be censored on the date of last disease assessment.

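### Progression that follows a recurrence may go unrecorded in patients who stop treatment: Protocol 6.3 ends their disease assessment and lists no stage, grade or N/M item

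*Protocol*

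**What the plan says.** Protocol 2.2 sets the objective: "To evaluate the proportion of patients with progressive disease at 3, 6, 12, 18, and 24 months". Section 10.1 defines recurrence and progression as different events. Recurrence is disease at the same or a lower stage than at screening. Progression is a rise in T stage, T2 or worse, nodal or distant disease, or a change from low to high grade.

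Section 6.3 follows every patient for survival, "New anticancer treatments initiated after disease recurrence", TURBT or fulguration, and cystectomy. It keeps cystoscopy, cytology and, where indicated, biopsy for patients who finished treatment and for one other group, those who "discontinued study product dosing due to reason other than disease recurrence/progression will have the following procedures performed". For the remainder it says: "If a patient has recurrent/progressive disease and discontinues study treatment, the above disease assessment procedures will be discontinued". Contact with them after that point can be by telephone. Section 3.1 sets the same end to assessment: "study termination, disease progression, or recurrence requiring treatment discontinuation, whichever occurs first".

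Other sections point the other way. Under 7.2.2, after stopping treatment "the patient will continue to be followed for study endpoints, unless consent for this is specifically withdrawn". Section 10.1 places disease monitoring in both treatment and follow-up, and has stage recorded when disease recurs or progresses. Section 11.8.3 sends recurrence and progression to the clinical assessments in the eCRF.

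SAP 7.2 runs time to progression from randomization, uses Kaplan-Meier estimates to 24 months, and adds: "If progression has not occurred in a patient, the date of last disease assessment will be used as the timepoint for censoring". It does not make recurrence the end of observation.

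**The concern.** A patient can recur at the same stage and progress later, and that later event falls within the endpoint as both documents define it. For a patient who recurs and stops treatment, 6.3 removes the examinations that would find it. The remaining follow-up items record that a TURBT or cystectomy took place, but not what the pathology showed. Under 7.2.1, a recurrent patient may stay on treatment if the investigator judges this best, so whether later progression can be observed depends partly on a decision made after randomization.

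Censoring near the recurrence is harmless only if recurrent patients carry the same later risk of progression as those who remain disease-free. If their risk is higher, the progression estimates are too low. This can begin at the 6-month time point, for a patient who recurs at month 3. The estimates would then describe mainly progression as a first event, plus progression in patients kept on treatment. If the vaccine prevents recurrence and thereby progression, that benefit could be hidden. A different estimator, such as cumulative incidence, cannot recover events that were not collected.

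**Working it through.** **1. The plan's own figure.** The documents give no rate, sample size or power for progression. The only planning rates are 60% (control) and 90% (vaccine) 1-year DFS, in Protocol 12.6.2. Exact enumeration of the one-sided Fisher test at 0.10 with 23 evaluable per arm (SAP section 4) gives 80.8% power, against the stated 80%. The rates are therefore used as they stand.

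**2. Patients who could leave assessment by month 12.**
- Control: 25 × 0.40 = 10.
- Each vaccine arm: 25 × 0.10 = 2.5.

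These are upper bounds. They include deaths and first-event progressions, and only patients who recur and stop treatment lose assessment.

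**3. Effect on the planned Kaplan-Meier estimate.** Assumptions, none of them in the documents:
- Hazards are constant, and deaths are not modelled separately.
- The progression hazard before recurrence is λ = 0.002 per month in every arm, and kλ after recurrence.
- Every patient who recurs leaves assessment at that point.

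With S the 1-year DFS and T in months:
- Hazard of any first event: h = −ln(S)/12, which is 0.04257 (control) and 0.00878 (vaccine).
- Recurrence hazard: r = h − λ, which is 0.04057 and 0.00678.
- Estimate with censoring at recurrence: 1 − exp(−λT). At 24 months this is 1 − exp(−0.048) = 4.7% in every arm.
- True probability of progression: 1 − exp(−hT) − r[exp(−kλT) − exp(−hT)]/(h − kλ).

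Control with k = 3 and T = 24: exp(−hT) = 0.36 and exp(−0.144) = 0.866, so the result is 0.640 − 0.04057 × 0.506/0.03657 = 0.640 − 0.561 = 0.079.

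| Months | k | Estimate, every arm | True, control | True, vaccine | Shortfall in points, control / vaccine |
|---|---|---|---|---|---|
| 12 | 3 | 2.4% | 3.3% | 2.6% | 0.9 / 0.2 |
| 12 | 5 | 2.4% | 4.3% | 2.7% | 1.9 / 0.3 |
| 24 | 1 | 4.7% | 4.7% | 4.7% | 0 / 0 |
| 24 | 3 | 4.7% | 7.9% | 5.4% | 3.2 / 0.7 |
| 24 | 5 | 4.7% | 10.9% | 6.0% | 6.2 / 1.3 |

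**4. Which way the illustration leans.** It removes every recurrent patient, including those who recur after month 12. Patients who stay on treatment keep their scheduled cystoscopies. Read literally, 6.3 also keeps cystoscopy for patients who completed treatment, whose last dose is at Week 52. For given hazards, the shortfall under the plan would be smaller than shown at 24 months.

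**The case against.** **Stage capture.** A reader might infer that stage and grade are never recorded after a recurrence, so that a later T2 finding cannot become a progression event. The documents do not support that. Sections 10.1 and 11.8.3 say that stage at progression is captured and that progression goes into the eCRF, and notes 9 and 15 to the Phase 2 schedule keep these patients in long-term follow-up. The eCRF itself is not among the documents, and a site could report such a finding. What stands is that none of these passages names a procedure or data item for this group, while 6.3 and 3.1 expressly stop the examinations.

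**Size.** A reader might take 10 control patients, suppose that 50% to 100% stop treatment and 10% to 30% of those progress, and reach 0.5 to 3.0 missed events, or 2 to 12 points on 25. The percentages are assumptions, the 10 is an upper bound, and dividing by 25 does not match the planned estimator. Kaplan-Meier does not count a censored patient as progression-free for the rest of follow-up.

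**Direction.** A greater loss in the arm with more recurrences is not a fact of the plan. It requires similar stopping rates and similar post-recurrence risk across arms.

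**Intent.** After treatment stops, care is at the physician's discretion, and 9.2 prohibits nothing in long-term follow-up. Choosing not to pursue progression under later therapies would be defensible. Neither document states that choice, and neither makes recurrence terminal for this endpoint.

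**Importance.** This is one secondary endpoint in an exploratory trial with 25 patients per arm, and SAP 5.5 confines p-values to the primary analysis. That limits the weight of the point but does not remove it.

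**Conclusion.** The gap is real but bounded. Protocol 6.3 and 3.1 conflict with 7.2.2, 10.1 and 11.8.3. Followed as written, the plan may miss progression in patients who recur during the roughly 12-month treatment period and then stop treatment, and SAP 7.2 censors them near the recurrence.

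Whether this biases the results depends on the later risk. If recurrence leaves the progression hazard unchanged, only events and precision are lost. If it raises the hazard, the estimates are too low: by about 3 points in control and 0.7 in a vaccine arm at 24 months for a three-fold hazard, and about 6 and 1.3 for five-fold. These sizes rest on the assumed 0.002 monthly hazard, the planned DFS rates and all recurrent patients leaving assessment. The difference between arms further assumes equal stopping behaviour and equal post-recurrence risk.

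The primary 1-year DFS endpoint is not affected, because the first recurrence already counts as an event. The point is worth correcting because the remedy is cheap.

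**What to change.** Reconcile Protocol 6.3 and 3.1 with 7.2.2, 10.1 and 11.8.3. For patients who recurred and stopped treatment, add to the 6.3 follow-up items the stage, grade, N/M status and date from any standard-of-care TURBT, biopsy, cystectomy or imaging. In SAP 7.2, state that progression counts whether or not a recurrence came first, and that such a staging result counts as a disease assessment for censoring. The SAP definition already runs from randomization to progression, so its part is clarification; the data fields are the substantive change.

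The cost is a few follow-up eCRF fields completed from existing reports, plus the SAP wording. No study cystoscopy or visit is added. The downside is that staging after recurrence follows local care rather than a fixed schedule, so some unequal ascertainment remains and should be acknowledged when the progression results are reported.
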